11.8 Guidelines for the treatment of study drug induced skin toxicity

Close monitoring of potential skin reactions is recommended at each planned visit and should be recorded and reported as an adverse event.

Although preclinical experiments demonstrated that buparlisib has no potential phototoxic effect, it is recommended to caution patients to avoid sun exposure during treatment with buparlisib, especially when they already have experienced rash or other skin toxicities. Patients should be advised to take measures to protect themselves from direct exposure to sunlight, including the wearing of sunglasses as well as the use of hats, long-sleeve shirts and long pants when outdoors.

11.9 Concomitant medications

In general, the use of any concomitant medication/therapies deemed necessary for the care of the patient is permitted (see Section Permitted concomitant therapy), except as specifically prohibited (see Section Prohibited concomitant therapy).

All medications (excluding study treatment and prior antineoplastic treatments), procedures and significant non-drug therapies (including physical therapy and blood transfusions) administered within 28 days prior to the administration of buparlisib through 30 days after the last dose of buparlisib will be recorded in the Concomitant medications. Medications include not only physician prescribed medications, but also all over-the-counter medications, herbal medications (prohibited, see Section below) and food or vitamin supplements. The investigator should instruct the patient to notify the investigational site about any new medications she takes after the start of the study drug.

The patient must be told to notify the investigational site about any new medications he/she takes after the start of the study drug. All medications (other than study drug) and significant non-drug therapies (including physical therapy and blood transfusions) administered during the study must be listed on the Concomitant Medications Sheet.

11.10 Permitted concomitant therapy

11.10.1 Corticosteroids

Corticosteroids may be used at limited doses, as they have limited impact on buparlisib metabolism. We recommend using corticosteroids at the smallest possible dose to control symptoms or cerebral edema and mass effect, and discontinue if possible. Please also refer to the Investigator's Brochure for the latest recommendations and findings.

Caution is also warranted for potential interaction with hyperglycemia.

11.10.2 Drugs that are metabolized by CYP450 enzymes

In vitro metabolism studies performed to examine the reversible and metabolism-dependent inhibition of CYP450 enzymes showed that buparlisib is a weak, reversible inhibitor of CYP3A4/5, CYP2C8, CYP2C9 and CYP2C19. Note that with the data available, it is not possible to confirm whether such interactions will occur in patients. Therefore, investigators, at their discretion, may administer concomitant medications known to be metabolized by CYP3A4/5, CYP2C8, CYP2C9 and CYP2C19. Patients receiving such medications must be monitored for potentiation of toxicity due to any individual concomitant medications, and may require dose titration or reduction of the drug substrate.

MEMORIAL SLOAN-KETTERING CANCER CENTER IRB PROTOCOL

IRB#: 14-177 A(5)

Refer to Appendix 2: List of CYP450 substrates to be used with caution. Particularly, caution is advised when buparlisib is co-administered with drugs that are sensitive substrates and/or have a narrow therapeutic index (e.g., SSRI).

Concomitant treatment of buparlisib with weak or moderate inducers of CYP3A4 is permitted, however, duration of concomitant treatment should be kept as short as possible (e.g., less than 1 week), or fully avoided whenever possible. Note that coadministration of buparlisib with strong inducers is prohibited (see below).

11.10.3 Non-enzyme Inducing Anti-epileptic drugs

Non-enzyme inducing anti-epileptic medication (Non-EIAED) is allowed, except for those listed in Appendix 1.

11.10.4 Bisphosphonates

The use of bisphosphonates for bone metastatic disease is allowed.

11.10.5 Palliative radiotherapy

Local radiotherapy for analgesic purposes or for lytic lesions at risk of fracture may be carried out if required. Radiation to the central nervous system is NOT allowed during the trial. If a patient required palliative radiation involving the CSF space (vertebral spine radiation) prior authorization through the principal investigator is needed. Whenever possible, these patients should have a tumor assessment of the lesion(s) before receiving the radiotherapy in order to rule out progression of disease. No dose modification of study treatment is needed during radiotherapy but should be monitored with caution.

11.10.6 Drugs with a conditional or possible risk to induce Torsades de Pointes

If a patient, after enrollment in the study, requires the concomitant use of any QT prolonging medication with a possible or conditional risk for Torsades de Pointes included in Appendix 4, then investigators, at their discretion, may co-administer such medications. Patients receiving such medications must however be closely monitored.

11.10.7 Gastric protection agents

Buparlisib is characterized by a pH-dependent solubility. Medicinal products that alter the pH of the upper Gastro-Intestinal (GI) tract may alter the solubility of buparlisib and hence its bioavailability. These agents include, but are not limited to, proton-pump inhibitors (e.g., omeprazole), H₂-antagonists (e.g., ranitidine) and antacids. Buparlisib should be dosed in a staggered manner at least 1 hour before or 10 hours after dosing with medicinal products that may alter the pH of the upper GI tract.

11.10.8 Prohibited concomitant therapy

11.10.8.1 Other anticancer therapy

Anticancer therapy (chemotherapy, endocrine, biologic or radiation therapy, and surgery) other than the study treatments must not be given to patients while the patient is enrolled in the treatment portion of the trial. If such agents are required for a patient then the patient must be permanently discontinued from the treatment portion of the study.

11.10.8.2 Other investigational therapies

Other investigational therapies must not be used while the patient is on the study.

11.10.8.3 Hematopoietic growth factors

Prophylactic use of hematopoietic growth factors (e.g. erythropoietins, granulocyte colony-stimulating factor (G-CSF) and granulocyte macrophage colony-stimulating factor (GM-CSF)) are not permitted. However, in the event of an emergency (e.g. acute myelosuppression with infection), a patient may be given hematopoietic growth factors according to the investigator's judgment, and the sponsor should be notified as soon as possible. Subsequent secondary prevention use is permitted at investigator's discretion.

Patients who begin erythropoietin or darbepoetin therapy before randomization may continue this treatment at the discretion of the investigator.

11.10.8.4 Warfarin and coumarin derivatives

Therapeutic doses of warfarin sodium or any other coumarin-derivative anticoagulants are not permitted.

Buparlisib is a weak inhibitor of CYP2C8 and 2C9, the major metabolizing enzyme of warfarin. Despite the fact that the inhibitory signal was weak, an increase of 40-50% of warfarin exposure is possible and for a drug like warfarin, this might be clinically relevant.

11.10.8.5 Enzyme-inducing anti-epileptic drug (EIAED)

Use of enzyme-inducing anti-epileptic drug (EIAED) is not permitted. Refer to Appendix 1 for a list of prohibited EIAED.

If a patient is currently taking EIAED, they must have discontinued the EIAED therapy for at least two weeks prior to starting study drug.

If a patient is previously on a non-EIAED and needs to permanently change the anticonvulsant agent, but cannot change to another non-EIAED, the patient will be taken off buparlisib.

11.10.8.6 Drugs with a known risk for Torsades de Pointes

If a patient requires the concomitant use of any medication included in Appendix 3 entitled "List of Prohibited QT prolonging drugs" (i.e., drugs that are generally accepted by the Qtdrugs.org Advisory Board of the Arizona CERT to have a risk of causing Torsade de Pointes), study treatment must be delayed. Note that Appendix 3 lists drugs with a known risk for Torsades de Pointes (TdP) as well as sensitive CYP3A substrates (with narrow therapeutic index) with a possible or conditional risk for TdP. Study treatment administration must be interrupted as long as the patient requires therapy with the QT prolonging agent.

11.10.8.7 Moderate and strong CYP3A inhibitors and inducers

In vitro metabolism studies suggest that oxidative metabolism of buparlisib is predominantly mediated by CYP3A4 and UGT1A4. Coadministration of buparlisib with strong and moderate CYP3A4 inhibitors and inducers is predicted to respectively increase or decrease the systemic exposure to buparlisib.

Please refer to Appendix 1 for a list of prohibited drugs. Please note that this list may not be comprehensive.

11.10.8.8 Herbal medications

Herbal preparations/medications are not allowed throughout the study, as a potential drug-drug interaction is always possible. These herbal medications include, but are not limited to: St. John's wort, Kava, ephedra (ma huang), ginkgo biloba, dehydroepiandrosterone (DHEA), yohimbe, saw palmetto, and ginseng.

Patients should stop using these herbal medications at least 7 days prior to first dose of study treatment.

11.10.8.9 Hormonal contraception

Hormonal contraceptives may be affected by cytochrome P450 interactions, and are therefore not considered effective for this study, since induction of CYP3A4 may not be excluded in patients receiving buparlisib.

11.11 Liver Toxicity

11.11.1 Liver Toxicity Findings

A recent liver safety review across Novartis-sponsored trials with BKM120 identified several potentially drug-induced liver toxicity (DILI) cases (e.g. AST/ALT >3.0 x ULN and TBL >2.0 x ULN at any time during the treatment, regardless of causality). Upon medical review, most of these cases occurred in the context of disease progression in terminally ill, advanced cancer patients and/or were confounded by other causes. However, six of these DILI candidates were consistent with Hy's law criteria (e.g. AST/ALT >3.0x ULN and TBL >2.0xULN in the absence of cholestasis and other explanatory causes) with probable causal relationship to study treatment. Five of these cases were enrolled in study CBKM120F2302 in combination with fulvestrant, and one in combination with the investigational drug LDE225 (sonidegib). All patients have recovered upon treatment discontinuation except one patient for whom no data is available since the patient refused to return for safety follow-up.

Approximately 25 to 45% of patients treated with single agent BKM120 reported liver toxicity (all grades, regardless of study drug relationship, 100 mg/d dose) based on a search of multiple MedDRA event terms (e.g. SMQ preferred terms). The incidence of grade 3 and 4 events was approximately 10 to 30%. Liver function test (LFT) alterations observed during ongoing and completed studies have been mostly transaminase enzyme increases (ALT and/or AST). Data suggest a slightly higher rate of grade 3 and 4 liver enzyme elevations in Japanese patients (44%) in the [CBKM120X1101] study, however, the number of patients treated at 100 mg in this study was limited (n=9). Transaminase elevations typically occur during the first 6 to 8 weeks of treatment start.

Although transaminase increases are relatively common, only a few of the patients had other simultaneous observations related to impaired liver function (e.g. bilirubin increase or clinical symptoms).

Based on these findings, conservative inclusion criteria and guidelines to monitor and follow patients with LFT alterations (including dose and schedule modifications) have been implemented. Please refer to the respective inclusion/exclusion criteria and Table 11.0 in this protocol for more detailed guidelines.

11.11.1.2 Management of Hepatotoxicity (ALT and/or AST \geq 3.0x ULN and total bilirubin \geq 2.0x ULN) in patients receiving Buparlisib

Criteria for interruption and re-initiation of buparlisib treatment in case of the occurrence of AST, ALT or bilirubin increase are detailed in Section 11.2, Toxicity Management (Table 11).

Patients with clinically significant liver test abnormalities should perform liver-directed medical history, physical examination and other tests as medically indicated to assess potential relationship with study treatment and rule out other underlying causes (e.g. disease progression/obstruction, infection/hepatitis or other liver diseases, sepsis, metabolic diseases including diabetes, concomitant medications including herbals, alcohol, drug-drug interaction, cardiovascular disease/ischemia, other organ injuries, etc.). Any pre-existing liver conditions or risk factors should be reported in the respective medical history and concomitant medication CRF pages (if not done already).

All patients with ALT or AST $>$ 3.0 x ULN and total bilirubin $>$ 2.0 x ULN in the absence of cholestasis (elevation of ALP in patients without bone metastasis or if bone metastasis are present elevation of 5'-nucleotidase and ALP liver fraction) must be immediately withdrawn from buparlisib, and every attempt should be made to carry out locally the liver event follow-up assessments as described below:

- Inform the sponsor about the event immediately after its occurrence by reporting the event immediately in the clinical database if it meets the criteria for an AE or SAE.
- Evaluate if associated with the appearance or worsening of clinical symptoms of hepatitis or hypersensitivity such as fatigue, nausea, vomiting, right upper quadrant pain or tenderness, fever, rash or eosinophilia, or other organ involvement.
- Obtain fractionated bilirubin, serum Alkaline Phosphatase (ALP), creatine phosphokinase (CPK), lactate dehydrogenase (LDH), and blood count with differential to assess eosinophilia.
- Perform liver imaging (ultrasound, magnetic resonance, or computerized tomography) to evaluate liver disease including metastasis or new lesions, obstruction/compression, etc.
- Perform viral hepatitis and other serology tests:•
 - Hepatitis C (HCV) serology and viral RNA, Hepatitis B (HBV) serology and viral DNA, Hepatitis A (HAV) Immunoglobulin M (IgM) and HAV total
 - Hepatitis E (HEV) serology: IgM and IgG, viral RNA
 - Herpes Simplex Virus (HSV), Cytomegalovirus (CMV), Epstein-Barr viral (EBV) serology
- Verify and record the use of concomitant medications, acetaminophen, herbal remedies, and other over the counter medications, or putative hepatotoxins, on the concomitant medications report form.
- Consultation with a specialist(s) or a hepatologist(s) is recommended.
- Liver biopsy as clinically indicated to assess pathological change and degree of potential liver injury
- LFTs should be followed-up weekly until resolve to \leq grade 1, baseline or stabilization (no CTCAE grade change over 4 weeks) and outcome documented on the respective AE and lab chemistry pages.

11.11.1.3 Laboratory Evaluations

Hepatotoxicity follow-up testing will be performed when needed (refer to section

11.11.1.2) in patients receiving buparlisib.

Table 13 Clinical laboratory parameters collection plan

Test Category	Test Name
*Viral hepatitis serologic tests and other tests for hepatotoxicity follow-up *	HAAb, HBsAg, HBsAb HBcAb, HCV RNA or HDV RNA (where needed), HEAb, CMVAb, EBcAb, ALP, CPK, LDH, WBC (eosinophilia), and others.
* Hepatotoxicity follow-up testing/procedures will be performed locally (refer to Section 11.11.1.2: Management of hepatotoxicity (ALT and/or AST >3.0x ULN and total bilirubin >2.0x ULN) in patients receiving buparlisib and Viral hepatitis serology and other tests for hepatotoxicity follow-up.	

Viral Hepatitis serology and other tests for hepatotoxicity follow-up

Viral hepatitis serologic tests are performed confirm patient’s eligibility when needed per clinical judgment and specific patient’s clinical circumstances.

During study treatment, viral hepatitis serologic and other tests will be performed as per the guidelines of management of hepatotoxicity (ALT or AST >3.0x ULN and total bilirubin > 2.0x ULN) in patients receiving buparlisib, refer to Section 6.2.4.X Management of hepatotoxicity (ALT and/or AST >3.0x ULN and total bilirubin >2.0x ULN) in patients receiving buparlisib for details.

Viral hepatitis serology includes the following:

- Hepatitis B surface antigen, Hepatitis B Core Antibody (IgM) and viral DNA
- Hepatitis C serology and viral RNA
- Hepatitis D RNA (where needed)
- Hepatitis E IgM and IgG antibody and viral RNA

Obtain fractionated bilirubin, serum Alkaline Phosphatase (ALP), creatine phosphokinase (CPK), lactate dehydrogenase (LDH), and blood count with differential to assess eosinophilia.

Additional viral serology tests may include:

- Cytomegalovirus IgM antibody
- Epstein-Barr viral capsid antigen IgM antibody (or if unavailable, obtain heterophile antibody or monospot testing)
- Herpes Simplex Virus

12.0 CRITERIA FOR THERAPEUTIC RESPONSE/OUTCOME ASSESSMENT

12.1 Definitions of response

This study will use the Macdonald criteria (Macdonald, et al. 1990). Specific lesions must be evaluated serially, and comparative analysis of changes in the area of contrast enhancement, as well as the non-enhancing component, should be performed. As with the Macdonald criteria (Macdonald, et al. 1990), the product of the maximal cross-sectional enhancing diameters will be used to determine the size of the contrast-enhancing lesions.

MEMORIAL SLOAN-KETTERING CANCER CENTER IRB PROTOCOL

IRB#: 14-177 A(5)

- a. Measurable disease: Measurable lesions are defined as enhancing lesions that can be accurately measured in at least two dimensions ≥ 10 mm. All tumor measurements must be reported in millimeters.
- b. Non-measurable disease: All other lesions (or sites of disease), including small lesions (<10 mm with conventional techniques) are considered non-measurable disease.
- c. Cytologic Complete Response (CCR): Complete clearing of all malignant cells from ventricular or lumbar source based on cytology. A cytologic CR must be documented by two negative cytologies from ventricular or lumbar sources on consecutive occasions at least 4 weeks apart.

12.2 Guidelines for evaluation of measurable disease

1. Complete Response (CR): Complete disappearance of all measurable and non-measurable disease. No new lesions. All measurable and non-measurable lesions and sites must be assessed using the same techniques as baseline. Patients must be on no steroids.
2. Partial Response (PR): Greater than or equal to 50% decrease over the baseline in the sum of products of perpendicular diameters of all measurable lesions. No progression of non-measurable disease. No new lesions. All measurable and non-measurable lesions and sites must be assessed using the same techniques as baseline. The steroid dose at the time of the scan evaluation should be no greater than the maximum dose used in the first 8 weeks from initiation of therapy.
3. Stable/no response: Does not qualify for CR, PR, or progression. All measurable and non-measurable sites must be assessed using the same techniques as baseline. The steroid dose at the time of the scan evaluation should be no greater than the maximum dose used in the first 8 weeks from initiation of therapy.
4. Progression: 25% increase in the sum of products of all measurable lesions over smallest sum observed (or baseline if no decrease) using the same techniques as baseline, OR clear worsening of any non-measurable disease, OR appearance of any new lesion/site, OR clear clinical worsening or failure to return for evaluation due to death or deteriorating condition (unless clearly unrelated to this cancer).

12.3 Guidelines for patients with CSF disease

1. Complete Response (CR): Combination of CCR and complete disappearance of all measurable and non-measurable disease (if the participant had imaging abnormalities at enrollment). No new lesions. All measurable and non-measurable lesions and sites must be assessed using the same techniques as baseline. Patients must be on no steroids.
2. Partial Response (PR): Combination of CCR and stable size of all measurable and non-measurable disease (if the participant had imaging abnormalities at enrollment). No new lesions. All measurable and non-measurable lesions and sites must be assessed using the same techniques as baseline. Patients should be on a stable or reduced does of steroids.
3. Stable/no response: Tumor cells still present in CSF cytology and stable size of all measurable and non-measurable disease (if the participant had imaging abnormalities at enrollment). No new lesions. All measurable and non-measurable lesions and sites must be assessed using the same techniques as baseline. Patients should be on a stable or reduced does of steroids.

MEMORIAL SLOAN-KETTERING CANCER CENTER IRB PROTOCOL

IRB#: 14-177 A(5)

4. Progressive Disease (PD): 25% increase in the sum of products of all measurable lesions over smallest sum observed (or baseline if no decrease) using the same techniques as baseline, OR clear worsening of any non-measurable disease, OR appearance of any new lesion/site on imaging, OR clear clinical worsening or failure to return for evaluation due to death or deteriorating condition (unless clearly unrelated to this cancer) regardless of CSF cytology status.

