2.0 OBJECTIVES AND SCIENTIFIC AIMS

2.1 Primary Objective:

- To explore the therapeutic efficacy of buparlisib in patients with PCNSL and SCNSL as measured as progression free survival at 24 weeks (PFS24w)

2.2 Secondary Objectives:

- To explore the safety and tolerability of buparlisib in PCNSL and SCNSL patients by assessing the frequency and severity of adverse events
- To assess overall response rate (ORR) on MR imaging in patients with PCNSL and SCNSL receiving buparlisib
- To assess progression free survival at 12 weeks (PFS12w) and 48 weeks (PFS48w) in patients with PCNSL and SCNSL receiving buparlisib
- To assess the duration of response (DoR) and overall survival (OS) in patients with PCNSL and SCNSL receiving buparlisib
- To evaluate CSF pharmacokinetics of buparlisib by measuring drug concentration in serum and CSF samples

2.3 Exploratory Objectives:

- To correlate differences in drug response to PI3K pathway activation status through mutational and immunohistochemical analysis of PI3K pathway members such as but not limited to phospho-AKT, phospho-S6, phospho-4EBP1
- To characterize mutational abnormalities in paired tumor/germline DNA in PCNSL/SCNSL patients and correlated with drug response

- To correlated changes on ADC/DWI/perfusion MRI imaging to drug response
- To assess neurologic functioning using the Neurologic Assessment in Neuro-Oncology (NANO)

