6.1 Subject Inclusion Criteria

Patients eligible for inclusion in this study have to meet all the following criteria:

- Participants must be able to understand and be willing to sign a written informed consent document.
- Subjects must be at least 18 years of age on the day of consenting to the study.
- Histologically documented PCNSL or SCNSL. Patients with SCNSL need to have cytology or tissue biopsy documenting lymphomatous involvement of the CNS
- Patients must have relapsed/refractory PCNSL or relapsed/refractory SCNSL
- All patients need to have received at least one prior CNS directed therapy. There is no restriction on the number of recurrences.
- Patients with parenchymal lesions must have unequivocal evidence of disease progression on imaging (MRI of the brain or head CT) 21 days prior to study registration. For patients with leptomeningeal disease only, CSF cytology must document lymphoma cells and/or imaging findings consistent with CSF disease 21 days prior to study registration.
- Participants must have a Karnofsky performance status (KPS) of ≥ 50 .
- Participants must have adequate bone marrow and organ function shown by:

MEMORIAL SLOAN-KETTERING CANCER CENTER IRB PROTOCOL

IRB#: 14-177 A(5)

- Absolute neutrophil count (ANC) $\geq 1.5 \times 10^9/L$
- Platelets $\geq 100 \times 10^9/L$ and no platelet transfusion within the past 14 days prior to study registration
- Hemoglobin (Hgb) ≥ 9 g/dL and no red blood cell (RBC) transfusion within the past 14 days prior to study registration
- International Normalized Ratio (INR) ≤ 1.5
- Alanine aminotransferase (ALT) and aspartate aminotransferase (AST) ≤ 1.5 times the ULN.
- Serum bilirubin \leq upper limit of normal; or total bilirubin $\leq 2.0 \times$ the ULN with direct bilirubin within the normal range in patients with well documented Gilbert Syndrome.
- Participants must be able to take oral medication.
- Patients must be able to tolerate MRI scans.
- Patients must be able to tolerate lumbar puncture and/or Ommaya taps.
- Participants must have recovered to grade 1 toxicity from prior therapy.
- Participants must be able to submit 20 unstained slides from the initial tissue diagnosis for confirmation of diagnosis and correlative studies
- Life expectancy of > 3 months (in the opinion of the investigator)

Note: Prior autologous stem cell transplant as well as radiation to the CNS is **NOT** an exclusion criterion. Prior allogenic stem cell transplant **IS** an exclusion criterion.

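### Section 12.3 leaves some CSF-disease patients with an ambiguous response category or none, so the objective response rate can be wrong in either direction

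*Combined protocol and SAP*

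**What the plan says.** For a patient with leptomeningeal disease only, section 6.1 asks that "CSF cytology must document lymphoma cells and/or imaging findings consistent with CSF disease 21 days prior to study registration", so imaging can stand in for positive cytology. Its separate rule for secondary disease, "Patients with SCNSL need to have cytology or tissue biopsy documenting lymphomatous involvement of the CNS", accepts a biopsy and is not tied to the 21-day baseline. It therefore does not guarantee a positive CSF sample at entry.

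Section 12.1 describes CCR as "Complete clearing of all malignant cells from ventricular or lumbar source based on cytology" and then adds: "A cytologic CR must be documented by two negative cytologies from ventricular or lumbar sources on consecutive occasions at least 4 weeks apart". No sentence states that baseline cytology must have been positive.

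Section 12.3 defines PR in CSF disease as "Combination of CCR and stable size of all measurable and non-measurable disease (if the participant had imaging abnormalities at enrollment", and stable disease as "Tumor cells still present in CSF cytology and stable size of all measurable and non-measurable disease". Complete response (CR) needs CCR plus disappearance of any imaging abnormality. Progression (PD) rests on imaging or clinical worsening, whatever the cytology shows. Section 12.2, for measurable disease, defines PR instead as "Greater than or equal to 50% decrease over the baseline in the sum of products of perpendicular diameters of all measurable lesions", and its stable category takes every patient who fits none of the other three.

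Section 12.4 counts CR plus PR under either section, over all patients in the study. The secondary objective in section 2.2 is "To assess overall response rate (ORR) on MR imaging in patients with PCNSL and SCNSL receiving buparlisib", whereas note 2 to Table 6 says that response in CSF disease is read from the CSF.

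**The concern.** Response categories should place every assessable patient in exactly one category. Section 12.3 has no residual category, and its stable category presupposes tumour cells that section 6.1 does not require at entry. A patient in whom nothing happened could be counted as a responder, and a patient with real shrinkage could go uncounted.

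Either error enters ORR, the set of patients analysed for duration of response (section 12.9 starts the clock at first CR or PR), and the cross-tabulation of ORR with mutation and immunohistochemistry results in section 14.0. The trial is open-label, and section 12.8 bases progression on the investigator's assessment. Gaps in the response definition would therefore probably be filled case by case by people who know the patient's course.

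A second issue is that a 12.3 PR can occur on an unchanged MRI, yet it is pooled into a rate whose stated objective is response on MRI.

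**Working it through.** **Inputs.** N = 21 (section 14.0), which is the ORR denominator (section 12.4). Cycles last 28 days (section 9.0). CSF and imaging are taken on day 1 of odd cycles from cycle 3 (Table 6). The documents do not give the number of affected patients, so I assume k = 0 to 4. I also assume 6 true responders, to start from a column of Table 14.

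**1. The plan's own figures.** Exact (Clopper-Pearson) limits for x responders of n: lower = Beta quantile 0.025 with parameters (x, n − x + 1); upper = Beta quantile 0.975 with parameters (x + 1, n − x). For n = 21, x = 6 gives 11.28% to 52.18% and x = 8 gives 18.11% to 61.56%. All twelve limits in Table 14 reproduce, so the table is not in dispute.

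**2. Four courses set against section 12.3.**

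| Course | CR | PR | Stable | PD |
|---|---|---|---|---|
| A. Leptomeningeal only; cytology negative from entry; imaging unchanged | No, imaging findings persist | Only if two negatives suffice for CCR | No, needs tumour cells | No |
| B. Cytology stays positive; lesions shrink ≥50% but remain | No CCR | No CCR | No, size not stable | No |
| C. Cytology clears; lesions shrink but remain | No, lesions persist | Not literally, size not stable | No, needs tumour cells | No |
| D. Cytology clears; brain lesion unchanged | No, lesion persists | Yes | No | No |

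A is PR or unclassified. B has no category. C has none on a literal reading. D is classified, but as a PR where the MRI alone would be stable under 12.2.

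**3. Can course A be documented?** Day 1 of cycle c falls on study day 28(c − 1) + 1: day 57 for cycle 3 (week 8) and day 113 for cycle 5 (week 16). The gap is 56 days, more than the required 4 weeks. Two on-study negatives are available by week 16, or earlier if the screening sample counts as the first.

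**4. Effect on ORR.** Each patient moved in or out changes ORR by 1/21 = 4.8 points.

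| Counted responders | ORR | Exact 95% CI |
|---|---|---|
| 4 (two true responders unscored) | 19.0% | 5.4% to 41.9% |
| 5 (one unscored) | 23.8% | 8.2% to 47.2% |
| 6 (all correct) | 28.6% | 11.3% to 52.2% |
| 7 (k = 1 unchanged patient added) | 33.3% | 14.6% to 57.0% |
| 8 (k = 2) | 38.1% | 18.1% to 61.6% |
| 9 (k = 3) | 42.9% | 21.8% to 66.0% |
| 10 (k = 4) | 47.6% | 25.7% to 70.2% |

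**5. Effect on duration of response.** Take assumed true durations of 4, 6, 8, 10, 12 and 14 months: the median is (8 + 10)/2 = 9. Adding two patients at 2 months gives (6 + 8)/2 = 7. Adding two at 20 months gives (10 + 12)/2 = 11. The direction is not fixed.

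**6. Effect on the primary endpoint.** PFS at 24 weeks depends on PD or death (section 12.8). PR versus stable does not enter it, or the rule of at least 12 of 21 progression free in section 14.0.

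**The case against.** The strongest reply concerns course A. Section 12.1 speaks of clearing malignant cells, and cells never found cannot be cleared. On that reading the two negative samples are proof of a CCR and not its definition, so the unchanged patient is not a PR. This stands as far as it goes. A reader might infer that 12.3 certainly scores this patient as a responder, and the text does not support that. But the same reading leaves the patient with no category, which is still a defect, and courses B and C do not depend on it.

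It can also be said that clearance in one compartment with no progression in the other is a reasonable composite response for CSF disease. I accept that course D is a design choice and not an error. The mismatch is with the wording of section 2.2.

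Finally, cases may be few. Imaging-only entry applies to leptomeningeal-only disease, and course A must avoid progression to about week 16. Apart from the methotrexate series (26 months), the drug series in Table 1 report PFS of 2 to 5.7 months. ORR is secondary and carries no decision rule. All of this limits the weight of the point but does not close the gap.

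**Conclusion.** Section 12.3 is not exhaustive and can misclassify response in CSF-disease patients. Each affected patient moves ORR by 4.8 points, upward if an unchanged patient is called PR and downward if real shrinkage goes unscored. The number affected is not in the documents and may be zero; the 6 responders and k = 0 to 4 above are illustrations only.

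Three stronger conclusions are tempting and do not follow:

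- **ORR is necessarily inflated.** Courses B and C can lower it, so the net direction is undetermined.
- **Duration of response is lengthened.** The analysis set is distorted, but the median can move either way.
- **Response on MRI is not measured at all.** Patients under 12.2 are scored on imaging, and a 12.3 CR requires any baseline imaging abnormality to disappear. What the documents support is that the pooled ORR mixes imaging responses with cytologic responses on an unchanged MRI.

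The primary analysis is unaffected. This is a clarification that should be made before responses are scored.

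**What to change.** Amend section 12.3 as follows.

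1. Allow CCR only when baseline cytology was positive. State that baseline cytology is required for every patient scored under 12.3: Table 6 lists it at screening, but section 8.1 joins imaging and CSF evaluation by and/or.
2. Score patients with negative baseline cytology on imaging by section 12.2.
3. Make stable the residual category, as in 12.2. Before doing so, assign a category explicitly to shrinkage of at least 50% with positive cytology and to CCR with incomplete shrinkage, so that neither falls into stable by default.
4. Keep the composite ORR if it is wanted, but also report an MRI-only ORR by the 12.2 thresholds and a separate cytologic response rate. State the denominator of each, since a patient with no imaging abnormality at entry cannot show an MRI response.

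The cost is a few sentences and a short addition to the response summary. The MRI and CSF assessments are already scheduled in Table 6. The reported ORR may change slightly.
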